7.1.2 Noninvestigational Products

Not applicable.

7.1.3 Medical Devices

The following investigational medical device(s) provided by Amgen for use in this study are the prefilled syringe (PFS) during the DBTP and the autoinjector (AI) during OLTP ([Table 7-1](#)).

The erenumab PFS is a single-use, disposable, handheld manual injection device for fixed dose SC injection of 70 mg in a 1 mL deliverable volume.

The erenumab AI is a single-use, disposable, handheld manual injection device for fixed dose SC injection of either 70 mg or 140 mg in a 1 mL deliverable volume.

Additional details are in the IPIM.

Other noninvestigational medical devices may be used in the conduct of this study as part of standard care.

Noninvestigational medical devices (eg, syringes, sterile needles), that are commercially available are not usually provided or reimbursed by Amgen (except, for example, if required by local regulation). The investigator will be responsible for obtaining supplies of these devices.

Refer to [Section 7.1.7](#) for a list of prohibited medical devices.

7.1.4 Other Protocol-required Therapies

Not applicable.

7.1.5 Other Treatment Procedures

Not applicable.

7.1.6 Product Complaints

A product complaint is any written, electronic or oral communication that alleges deficiencies related to the identity, quality, durability, reliability, safety, effectiveness, or performance of a drug(s) or device(s) after it is released for distribution to market or clinic by either Amgen or by distributors and partners for whom Amgen manufactures the material.

This includes any investigational product(s) or device(s) (eg, the PFS or AI) provisioned and/or repackaged/modified by Amgen.

Approved

Any product complaint(s) associated with any investigational product(s) or device(s) supplied by Amgen are to be reported according to the instructions provided in the IPIM.

7.1.7 Excluded Treatments, Medical Devices, and/or Procedures During Study Period

Concomitant treatment with **up to 2** oral migraine preventive medication is allowed under the following conditions:

- (1) drug regimen (ie, formulation, frequency of use, dose) is stable ≥ 2 months prior to baseline period start
- (2) drug regimen is at generally accepted dose, frequency and route for its use in migraine
- (3) drug regimen is not anticipated to change during baseline period or postrandomization (ie, during the subject's study participation).

Examples of such medications include but are not limited to the following:

- Antiepileptics (eg, divalproex sodium, sodium valproate, topiramate, carbamazepine, levetiracetam).
- Angiotensin receptor blockers (eg, candesartan) or ACE inhibitors (eg, lisinopril).
- Beta blockers.
- Calcium channel blockers (verapamil, amlodipine, cinnarizine, lomerizine) or calcium antagonists (eg, flunarizine).
- Tricyclic antidepressants.
- Other antidepressants (eg, serotonin-norepinephrine reuptake inhibitors, selective serotonin-reuptake inhibitors).
- Other drugs used for migraine prevention (eg, **coenzyme Q10**, clonidine, guanfacine, methysergide, cyproheptadine, pizotifen, butterbur, feverfew, magnesium (≥ 500 mg/day), riboflavin (≥ 100 mg/day)).

Approved

Prohibited Medications	Time Period for Exclusion
Concurrent use of non-investigational anti-CGRP mAbs	Prior history of treatment with and throughout the study
Use of the following acute medications for the acute treatment of migraine: Barbiturates or butalbital-containing medication for > 4 days/month Short-acting opioids or short-acting opioid-containing medication for >15 days/month Long-acting opioids or long-acting opioid-containing medication Cannabidiol (CBD)-containing products anticipated to have a systemic effect (eg, ingested or inhaled products) > 4 days/month	2 months before the start of the screening period and throughout the study
Investigational medications	30 days or 5 half-lives before the start of the screening period and throughout the study
Botulinum toxin (in the head and/or neck region)	4 months before the start of the screening period and throughout the study
Prohibited Procedures or Devices	Time Period for Exclusion
For any indication Infusion rescue therapy (ie, steroids, valproate sodium, dihydroergotamine) Note: infusion rescue therapy may be allowed during DBTP if medically justified	During screening period or baseline period
For any indication Devices (such as stimulation devices), or procedures (such as nerve blocks, or psychotherapy).	3 months before the start of the screening period and throughout the study
Cognitive Behavioral Therapy Subjects on a stable, maintenance phase of a cognitive behavioral therapy (CBT) program for migraine are allowed. CBT is defined as stable, on a maintenance phase if subject has undergone ≥ 6 weekly or biweekly sessions of CBT administered by adequately trained psychologists and who, for at least 3 months before the start of the baseline period, only follow "booster" CBT sessions at a monthly, bimonthly or quarterly frequency.	3 months before the start of the screening period

Approved

7.2 Method of Treatment Assignment

Subjects will be randomized in a 1:1:1 allocation ratio, to erenumab 70 mg/mL SC every 4 weeks, erenumab 140 mg/mL SC every 4 weeks, or matching placebo, respectively, in a double-blind manner for nonopioid-treated cohort and opioid-treated cohort separately.

Approved

The randomization will be performed by **IRT**, and the randomization number will be assigned by **IRT** and appear on the **IRT** randomization document. The randomization number is different than the subject identification number and will not be utilized by the site as a subject identifier.

The randomization will be stratified by concomitant treatment with an oral preventive (Yes or No) in the nonopioid-treated cohort.

The randomization date is to be documented in the subject's medical record and on the enrollment CRF.

7.3 Blinding

This study has a 24-week DBTP and a 28-week OLTP. Treatment assignment will be blinded to all subjects, site personnel, and Amgen as described below. **During the 24-week DBTP, treatment assignment will be blinded to all subjects, site personnel, and Amgen. Following the DBTP, during the 28-week OLTP, study team members in direct contact with sites, investigators, and subjects will remain blinded to the initial dose level.**

7.3.1 Site Personnel Access to Individual Treatment Assignments

A subject's treatment assignment during DBTP is to only be unblinded by the investigator when knowledge of the treatment is essential for the further management of the subject on this study or may potentially impact the safety of the subject. Unblinding at the study site for any other reason will be considered a protocol deviation. It is encouraged that the Amgen Trial Manager be notified before the blind is broken unless the investigator believes that identification of the study treatment is required for a medical emergency. If this is not possible, the Amgen Trial Manager must be notified within 24 hours after breaking the blind. The date and reason that the blind was broken must be recorded in the source documentation and CRF, as applicable.

7.3.2 Access to Individual Subject Treatment Assignments by Amgen or Designees

Blinded individuals will not have access to unblinded information until the study is completed. Unblinding and potentially unblinding information is not to be distributed to study team members in direct contact with sites, investigators or subjects prior to the final analysis.

7.4 Dose Modification

7.4.1 Dose-cohort Study Escalation/De-escalation and Stopping Rules

There will be no dose changes or dose stopping rules as part of this protocol.

7.4.2 Dosage Adjustments, Delays, Rules for Withholding or Restarting, Permanent Discontinuation

7.4.2.1 Amgen Investigational Product: Erenumab or Matching Placebo

Dose adjustments are not permitted.

7.4.3 Hepatotoxicity Stopping and Rechallenge Rules

Refer to [Section 12.7](#) for details regarding drug-induced liver injury guidelines, as specified in the *Guidance for Industry Drug-Induced Liver Injury: Premarketing Clinical Evaluation, July 2009*.

7.5 Preparation/Handling/Storage/Accountability

Guidance and information on preparation, handling, storage, accountability, destruction, or return of the investigational product during the study are provided in the IPIM.

7.6 Treatment Compliance

Administration of investigational product will be conducted at sites or at home during scheduled time points.

Noncompliance is to be documented in the medical file and will be reflected in the electronic CRF. Noncompliant subjects are to be re-educated on the importance of adhering to the investigational product administration schedule and reminded that repeated cycles of noncompliance could be a reason for discontinuation of study treatment.

7.7 Treatment of Overdose

Overdose with this product has not been reported. No specific antidote exists. In the case of an overdose, the subject should be treated symptomatically and supportive measures implemented as necessary.

7.8 Prior and Concomitant Treatment

7.8.1 Prior Treatment

For prior migraine preventive medications ending 2 months prior to start of baseline, therapy name, indication, dose, unit, frequency, start and stop dates will be collected in the prior migraine preventive medication CRF.

Approved

For all other prior therapies that were being taken/used within 120 days prior to screening through the signing of the informed consent, therapy name, start and stop dates will be collected in the concomitant medication CRF.

7.8.2 Concomitant Treatment

Throughout the study, investigators may prescribe any concomitant medications or treatments deemed necessary to provide adequate supportive care except for those listed in [Section 7.1.7](#).

Concomitant therapies are to be collected from screening through the end of study.

Concomitant medication that is taken to treat headaches or migraine symptoms acutely and/or may lead or contribute to MOH will be reported in the eDiary.

All other concomitant medications will be reported on the Concomitant Medications electronic case report form (eCRF) including any allowable concomitant migraine preventive medication.

8. Discontinuation Criteria

Subjects have the right to withdraw from investigational product and/or other protocol-required therapies, protocol procedures, or the study as a whole at any time and for any reason without prejudice to their future medical care by the physician or at the institution.

The investigator and/or sponsor can decide to withdraw a subject(s) from investigational product, device, and/or other protocol-required therapies, protocol procedures, or the study as a whole at any time prior to study completion for the reasons listed in [Sections 8.1, 8.2.1, and 8.2.2](#).

8.1 Discontinuation of Study Treatment

Subjects can decline to continue receiving investigational product and/or other protocol-required therapies or procedures at any time during the study but continue participation in the study. If this occurs, the investigator is to discuss with the subject the appropriate processes for discontinuation from investigational product or other protocol-required therapies and must discuss with the subject the possibilities for continuation of the Schedule of Activities (see [Table 2-1](#)) including different options of follow-up (eg, in person, by phone/mail, through family/friends, in correspondence/communication with other treating physicians, from the review of medical records) and collection of data, including endpoints, adverse events, and device-related events, as applicable and must document this decision in the subject's

medical records. Subjects who have discontinued investigational product and/or other protocol-required therapies or procedures should not be automatically removed from the study. Whenever safe and feasible, it is imperative that subjects remain on-study to ensure safety surveillance and/or collection of outcome data.

Subjects who permanently discontinue investigational product during the DBTP are to continue eDiary entry and to complete the remaining study visits through the week 24/ET visit for the assessment of primary and secondary endpoints.

Subjects who permanently discontinue investigational product during the OLTP are to complete the study procedures for the week 52 End of Study visit.

Reasons for removal from protocol-required investigational product(s) or procedural assessments include any of the following:

- Decision by Sponsor
- Lost to follow-up
- Death
- Ineligibility determined
- Protocol deviation
- Noncompliance
- Adverse event
- Subject request
- Pregnancy

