Product complaints	X	X	X	X	X	X	X	X	
Concomitant therapies review	X	X	X	X	X	X	X	X	

Footnotes after last page of table.

Approved

Table 2-2. Schedule of Activities - Study Visits Through Open-label Treatment Period

	Treatment Period								
	Open-label Treatment Period (28 Weeks)								
PROCEDURE	Wk 24 (OLTP Entry Visit)	Wk 28	Wk 32	Wk 36	Wk 40	Wk 44	Wk 48	Wk 52/ EOS ^a	Notes
LABORATORY ASSESSMENTS									
Urine pregnancy test (females of childbearing potential only) ^d	X	X			X			X	
Urine drug test	X (to be performed at the discretion of the investigator)								
Chemistry	X (to be performed at the discretion of the investigator)							X	
CLINICAL OUTCOME ASSESSMENTS/PATIENT-REPORTED OUTCOMES									
Site re-assigns eDiary to subject					X				
eDiary					X (Daily)				Daily during assessment study months
Subject brings eDiary to center for use during visit or to return								X	Sites should retain eDiary at EOS visit
MPFID					X (Daily)				Daily during assessment study months
HIT-6								X	eDiary in clinic
MFIQ								X	eDiary in clinic
MIDAS								X	eDiary in clinic

Footnotes after last page of table.

Approved

Table 2-2. Schedule of Activities - Study Visits Through Open-label Treatment Period

	Treatment Period								
	Open-label Treatment Period (28 Weeks)								
PROCEDURE	Wk 24 (OLTP Entry Visit)	Wk 28	Wk 32	Wk 36	Wk 40	Wk 44	Wk48	Wk 52/ EOS ^a	Notes
STUDY TREATMENT									
Subject receives training on usage of autoinjector	X								
Self-administration of investigational product at clinic	X	X			X				
Self-administration of investigational product at home			X	X		X	X		
Study staff dispenses and/or reconciles investigational product		X			X			X	
Amgen investigational product ^e	X	X	X	X	X	X	X		Autoinjectors

Page 3 of 3

BP = blood pressure; DBTP = double-blind treatment period; eDiary = electronic diary; EOS = end of study; ET = early termination; HIT-6 = Headache Impact Test-6; HR = heart rate; **IRT = Interactive Response Technology**; MFIQ = Migraine Functional Impact Questionnaire; MIDAS = Migraine Disability Assessment; MPFID = Migraine Physical Function Impact Diary; OLTP = open-label treatment period; RR = respiratory rate

^a A subject who discontinues investigational product during the OLTP or who completes the study will perform the week 52/EOS visit assessments. Subjects who early terminate will complete the assessments approximately 28 (+3) days after the last dose of investigational product.

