
 • To explore the effect of erenumab compared with placebo on the subject's assessment of the change in clinical status since the start of treatment 	
 • Change in clinical status as measured by the Patient's Global Impression of Change (PGIC) as assessed by the subject at month 6 of the DBTP

 • To explore the effect of erenumab compared to placebo on the change from baseline in allodynia symptoms 	
 • Change from baseline in Allodynia Symptoms Checklist-12 (ASC-12) score at assessment time points
Exploratory (Open-label treatment period)	

 • To explore the rate of MOH relapse in the end of open-label treatment period (OLTP) 	
 • MOH relapse at year 1, defined as both mean monthly AHMD \geq 10 days over months 11, 12, and 13 (week 41 through 52) AND mean MHD \geq 14 days over months 11, 12, and 13 (week 41 through 52) in subjects who achieved MOH remission at month 6 of the DBTP Note: This endpoint will be analyzed among subjects who were treated with erenumab throughout the entire study

 • To explore absence of MOH at end of OLTP 	
 • Absence of MOH at end of study as defined by mean monthly AHMD $<$ 10 days over months 11, 12, and 13 (week 41 through 52) OR mean MHD $<$ 14 days over months 11, 12, and 13 (week 41 through 52)

 • To explore sustainability of MOH remission during OLTP 	
 • Sustained absence of MOH over 1 year as defined by absence of MOH over the DBTP (months 1, 2, and 3 [week 1 through 12], OR months 4, 5, and 6 [week 13 through 24]) AND OLTP (months 11, 12, and 13 [week 41 through 52]).

Approved

Objectives	Endpoints
	
Note: “Absence of MOH” is achieved when mean monthly AHMD < 10 days OR mean MHD < 14 days over the respective 3-month period
 
This endpoint will be analyzed among subjects who were treated with erenumab throughout the entire study

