5.4.2 Monthly Intervals for Efficacy Endpoints Derived From Daily Diary Collection

The (4-week) monthly intervals for efficacy endpoints derived from daily eDiary collection will be determined based on each subject's monthly IP dosing dates. When an IP is missed, discontinued, or no longer required, a 28-day monthly interval will be used. Any eDiary data occurring after EOS date will not be included in the analysis.

Applicable efficacy endpoints utilizing the monthly intervals in [Table 5-1](#) include:

- Monthly migraine days (MMD)
- Monthly headache days (MHD)
- Monthly migraine-free days
- Monthly opioid/opioid-containing medication days
- Monthly acute headache medication days (AHMD)
- Monthly headache days with at least moderate pain intensity
- Monthly acute migraine-specific medication days
- Monthly average headache pain intensity
- Monthly average MPFID physical impairment domain score
- Monthly average MPFID impact on everyday activities domain score

Table 5-1. Monthly Interval for Efficacy Endpoints Derived From Daily Diary Collection

Study Period	Assessment Timepoint	Monthly Interval	
		Start Date (Day)	End Date (Day)
Baseline Period	Baseline	Device ready for entry date ^d	Day prior to study day 1
Double-blind Treatment Period	Week 4 (Month 1)	Study Day 1	Week 4 dose date – 1 ^b
	Week 8 (Month 2)	Week 4 dose date ^a	Week 8 dose date – 1 ^b
	Week 12 (Month 3)	Week 8 dose date ^a	Week 12 dose date – 1 ^b
	Week 16 (Month 4)	Week 12 dose date ^a	Week 16 dose date – 1 ^b
	Week 20 (Month 5)	Week 16 dose date ^a	Week 20 dose date – 1 ^b
	Week 24 (Month 6)	Week 20 dose date ^a	Week 24 dose date – 1 ^b
Open-label Treatment Period	Week 44 (Month 11)	Week 40 visit date ^c	Week 44 dose date – 1 ^b
	Week 48 (Month 12)	Week 44 dose date ^a	Week 48 dose date – 1 ^b
	Week 52 (Month 13)	Week 48 dose date ^a	Start date (day) + 27

^a Start Date (Day) = End date (day) of previous monthly interval + 1 if IP dose date is not available

^b End Date (Day) = Start date (day) of current monthly interval + 27 if IP dose date is not available

^c eDiary will be re-activated at the week-40 visit **during OLTP** irrespective of IP dose status. **Week 40 visit date will be determined by week 40 dose date. If week 40 dose date is missing, week 40 clinic visit date will be used instead. If dose date or clinic visit date of the week was missing, the target date of the week would be used to determine the start date or end date.**

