9.5.4 Analyses of Exploratory Efficacy Endpoints in Open-label Treatment Period

For the OLTP of the study, descriptive summaries of efficacy endpoints will be tabulated by visit based on observed data without imputation.

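### Subjects who leave the open-label period before about week 40 have no month 11–13 diary data, and the observed-data-only rule drops them from the 1-year MOH summaries

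*Protocol*

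**What the plan says.** Protocol 8.1 treats the two periods differently. For the double-blind period (DBTP): "Subjects who permanently discontinue investigational product during the DBTP are to continue eDiary entry and to complete the remaining study visits", up to week 24. For the OLTP: "Subjects who permanently discontinue investigational product during the OLTP are to complete the study procedures for the week 52 End of Study visit". Table 2-2 footnote a repeats this, "A subject who discontinues investigational product during the OLTP or who completes the study will perform the week 52/EOS visit assessments", and adds: "Subjects who early terminate will complete the assessments approximately 28 (+3) days after the last dose of investigational product". Protocol 9.1.3 gives similar timing for permanent discontinuation from the study. No passage gives a date for a subject who stops IP in the OLTP but remains on study. The same section 8.1 also says: "Whenever safe and feasible, it is imperative that subjects remain on-study to ensure safety surveillance and/or collection of outcome data".

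On the diary, Table 2-1 has sites keep the eDiary at week 24, and Table 2-2 has it reassigned at week 40 for daily use to week 52. SAP Table 5-1 footnote c expects re-activation at week 40 "irrespective of IP dose status", and SAP 5.4.2 uses 28-day intervals where IP has been discontinued.

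On analysis, SAP 9.5.4 says that OLTP "descriptive summaries of efficacy endpoints will be tabulated by visit based on observed data without imputation". SAP 8.3.2 counts missing dichotomous outcomes in the DBTP as nonresponse. For two of the three 1-year endpoints, relapse and sustained absence of medication overuse headache (MOH), protocol 4.1 and SAP 2.1 add a note: "This endpoint will be analyzed among subjects who were treated with erenumab throughout the entire study". Absence of MOH at end of study has no such note.

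**The concern.** The SAP expects months 11–13 diary data from people off drug, but no protocol instruction clearly produces them. In the DBTP the site is told to keep the diary going. In the OLTP it is told only to do the End of Study assessments, and the diary is not in the subject's hands between weeks 24 and 40. The pointer in 8.1 to continued follow-up is to Table 2-1, which covers the DBTP only.

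A subject in remission at month 6 who leaves the study at, say, week 32 then appears in neither the numerator nor the denominator of the 1-year summaries. If some leave because headache has returned, the reported results describe a selected group. The handling also changes between month 6 (missing is failure) and year 1 (missing is dropped), so the two remission percentages cannot be compared directly.

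**Working it through.** **Plan's own figures.** The plan states no figure for the OLTP endpoints. Its DBTP power reproduces and is not in question: 183 × 0.8 = 146.4 per arm, 33.1% versus 50.5%, two-sided 0.05 chi-squared test, gives 85.9% against the stated 85%.

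**Timing.** Inputs: dose day = 7 × week + 1; End of Study 28 to 31 days after the last dose (Table 2-2 footnote a, early terminators); diary from the week 40 visit, day 7 × 40 + 1 = 281; at least 14 diary days for a usable month (SAP 8.3). One usable month among months 11–13 is enough under SAP 8.3.3. That rule is written for the mean monthly value, and I assume it carries over to MOH status derived from that mean.

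| Last OLTP dose | Dose day | End of Study day | Diary days | Usable months of 11–13 |
|---|---|---|---|---|
| Week 24 | 169 | 197–200 | 0 | 0 |
| Week 28 | 197 | 225–228 | 0 | 0 |
| Week 32 | 225 | 253–256 | 0 | 0 |
| Week 36 | 253 | 281–284 | 0–3 | 0 |
| Week 40 | 281 | 309–312 | 28–31 | 1 |
| Week 44 | 309 | 337–340 | 56–59 | 2 |
| Week 48 | 337 | 365–368 | 84–87 | 3 |

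A subject who leaves after a last dose at week 36 or earlier contributes nothing. Only the last row falls inside the SAP week 52 window (day 352 to 379) for HIT-6, MFIQ and MIDAS.

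**Effect on relapse (all rates assumed).** Let s be the share of month-6 remitters without data, a the relapse rate in those observed, and b the rate in those not observed. The observed-only figure is a. With everyone followed it is (1 − s)a + sb, so the gap is s(b − a).

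- With s = 10–30%, a = 10–20% and b = 30–70%, observed relapse is 10–20%, against 12–35% with full follow-up.
- Smallest gap: 0.10 × (0.30 − 0.20) = 1 point. Largest: 0.30 × (0.70 − 0.10) = 18 points.
- If b = a the gap is zero; if b < a it reverses.
- Counting all missing as failures gives (1 − s)a + s: from 0.9 × 0.10 + 0.10 = 19% to 0.7 × 0.20 + 0.30 = 44%.

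**Scale.** At the planning rates and the protocol's 20% DBTP dropout, month-6 remitters number about 183 × 0.8 × 0.505 = 74 (70 mg) and 183 × 0.8 × 0.641 = 94 (140 mg), before optional OLTP entry.

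**Change of rule (assumed counts).** Of 100 OLTP entrants, 20 leave before week 40 and 60 of the other 80 are in remission. Observed data give 60/80 = 75%; the month-6 rule gives 60/100 = 60%.

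**The case against.** A reader might infer that the documents flatly contradict each other and that the 1-year endpoints are estimated only in people who stayed on drug. The visit rules do not support that. The protocol separates stopping IP from leaving the study: 8.1 wants subjects kept on study, 8.2.2 does not list stopping IP as a reason for removal, and the 28 (+3) day timing is written for early terminators. Section 8.1 can be read as week 52 procedures at week 52, which fits the SAP footnote. A subject who stops at week 32, stays on study and receives the diary at week 40 does have data. Even an early terminator whose last dose was at week 40 or 44 supplies one or two usable months. This stands, and it narrows the certain data loss to people who leave the study before about week 40.

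The population note also matters. Read literally, it excludes anyone who stopped erenumab from the relapse and sustained-absence endpoints by definition, whatever the visit rules. It may instead mean only that placebo switchers are excluded; the documents do not say. Either way, early leavers are not counted. Absence of MOH at end of study has no note, so the missing-data problem is plainest there.

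A reader might also take these endpoints as the trial's only evidence on durability. They are not: sustained remission over months 1–3 and 4–6 is placebo-controlled, formally tested and analysed with nonresponse imputation.

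Finally, SAP 9.2 already tabulates OLTP discontinuations with reasons, though not among month-6 remitters. Labelling everyone without data as relapsed would also assert an event nobody observed. That is fair, and it is why the relapse figure below is called a bound.

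**Conclusion.** The point holds in a limited form. The OLTP instructions omit the diary and remaining visits, leave the timing open for subjects who stop IP but stay, and do not match what the SAP expects at week 40. Subjects who leave before about week 40 have no usable month 11–13 data and are dropped. Absence of MOH at end of study is then estimated only in subjects still on study from week 40. So are relapse and sustained absence if the note excludes only placebo switchers; if it is literal, stoppers are outside those two endpoints by definition.

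The 1 to 18 point understatement of relapse rests wholly on assumed rates. It requires leavers to do worse than stayers, which is plausible but not shown, since the reasons for stopping in 8.1 also include adverse event, pregnancy, noncompliance and sponsor decision. The endpoints are exploratory and descriptive. The primary analysis, its power and its type I error are untouched.

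**What to change.** 1. In SAP 9.5.4, keep the observed-data table. Beside it, for absence of MOH at end of study and for sustained absence over 1 year, add a summary over all eligible subjects with at least one OLTP dose, counting those without month 11–13 data as not in remission. For relapse, take erenumab-randomised month-6 remitters who entered the OLTP. Report observed relapse, the number without data with their reasons for stopping, and the figure that counts them as not in remission, labelled as a bound because relapse was not observed.
2. State which reading of the note on erenumab treatment defines the population for relapse and sustained absence.
3. Reconcile protocol 8.1, Table 2-2 footnote a and 9.1.3 with SAP Table 5-1 footnote c on eDiary and visit data collection for subjects who stop IP in the OLTP but agree to stay on study.

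Items 1 and 2 cost SAP wording and a small set of added summaries from data already collected. The added figures are deliberately conservative and will look less favourable. Item 3 is a protocol clarification and needs no change to treatment.
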